5.4.3 Electrocardiograms (ECGs)

A standard 12-lead ECG will be obtained on all subjects at baseline (within 30 minutes prior to injection of LS301), 5-10 minutes post injection, and prior to discharge at 60 minutes.

The following table lists criteria for normal limits and clinically notable limits for ECGs in adults.

ECG Variables	Normal Limits (msec)		Notable Limits (msec)	
	Low	High	Low	High
PR interval	120	200	<120	>200
QRS interval	50	100	< 50	>100
RR interval	600	1000	<600	>1000
QT interval	No lower limit	≥ 460	No lower limit	≥ 460

5.4.4 Identification of Blood half-life of LS301

LS301 half-life will be determined using 500 μ L of blood collected at the same time as the CBC and CMP at baseline, 60 minutes post-injection, and one hour before surgery. These blood samples for research use will be drawn into pink top light-protected tubes, brought to the [name] lab for analysis, to identify the concentration of LS301 and determine of the half-life of the agent.

5.5 Risks and Adverse Event Monitoring

A potential risk specific to this experiment procedure is the injection of LS301. The imaging agent is not known to cause any serious adverse events in preclinical models. However, it is possible that some patients may experience mild reactions similar to those they might experience related to OctreoScan (a nuclear (SPECT) imaging agent) such as dizziness, fever, changes in liver enzymes, and nausea. The dose escalation procedure will allow us to monitor these reactions from low to high doses of LS301. There are other experimental tumor targeted imaging agents currently being evaluated in human patients (see the table below). Most of them either user antibodies tagged with ICG or dye-labeled biomolecule.

List of imaging agents under clinical investigation for image-guided surgery

Sl no	Agent	Clinical Trial	Trial type	Cancer type	Adverse reactions
1	Cetuximab IRDye800	NCT01987375	Phase 1 dose escalation study	Head and neck	Yes, in humans ⁶⁹ and monkeys ⁷⁰
2	Panitumumab IRDye 800	NCT02415881	Phase 1 safety/efficacy study	Head and neck	No reports found
3	Bevacizumab-800CW	NCT01508572 NCT02583568	Phase 1 Phase 2	Breast	No reports found. None reported for PET version ⁷¹
4	ICG and goggle	NCT02316795	Pilot	Breast and Melanoma	None reported ⁴³
5	ICG and Fluobeam	NCT01738217	Phase 1 and Phase 2	Liver	No reports found
6	BLZ 100 and Fluobeam	NCT02097875	Phase 1 dose escalation	Skin cancer	None in humans ⁷² and dogs ⁷³
7	BLZ 100 and unspecified system	NCT02234297	Phase 1 safety	Glioma	None in humans ⁷² and dogs ⁷³

The risks from the CVG system are extremely low. The system does not come into contact with the test subject. It utilizes safe invisible NIR light between 700 and 900 nm at a very low fluence rate ($\leq 25 \text{ mW/cm}^2$). This imaging system meets the US FDA definition of a “non-significant risk” device, and indeed could be considered “equivalent” to the Spy™ system, which has already obtained US FDA approval as a non-significant risk device.

The US FDA limit for NIR exposure is 10,000 mW/cm² and the current system utilizes 2.5-25 mW/cm² for a total duration of less than 30 minutes in the initial imaging and 10 minutes per subsequent imaging segments. This is equivalent to the current NIR dose emitted from the standard 5-lantern surgical lights commonly used in the operating room.

Patient safety monitoring for adverse events as a result of this study will be conducted as described in Section 5.4 above. Any reportable adverse event will be reported in accordance to Washington University HRPO regulations (see Section 6.0) for phase 1A. Any reportable adverse event in phase 1B/phase 2 will be reported in accordance to UTSW HRPP/IRB guidelines (see Section 6.0).

5.6 Collection of Specimens for Research Analyses (Phase 1B and Phase 2 ONLY)

5.6.1 Identification of Blood Proteins that Bind LS301

Five mL of blood collected at the same time as the CBC and CMP at baseline, 60 minutes post-injection, and one hour before surgery will be used to identify the predominant blood proteins that bind LS301 and mediate the bioavailability of the agent. This research blood will be drawn into a pink top light-protected tube and brought to the [name] lab.

5.6.2 Determination of LS301-Associated Biomarkers in Breast Cancer Tissue

After surgical removal of the cancer, the second (non-operating) surgeon will examine the tissue with the goggles and an additional ink will be used to identify any LS301 fluorescence in the surgical margin. This surgeon will then use the goggles to procure cores from the inked and sectioned specimens in surgical pathology. These cores will then be frozen and delivered to the biospecimen core for accessioning, processing, and storage. The specimens will then be analyzed to identify LS301-associated biomarkers.

5.7 Data Submission Schedule

Case report forms with appropriate source documentation will be completed according to the schedule listed in this study.

Case Report Form	Submission Schedule
Original Consent Form	Prior to registration
On Study Form Medical History Form	At the time of study entry
LS301 Injection Form	After injection
Surgery Form	After surgery
Follow-Up Labs Form	30 days after injection
Toxicity Form	Continuous
Death Form	Time of death
MedWatch Form	As described in Section 6.0

5.7.1 Adverse Event Collection in the Case Report Forms

All adverse events that occur beginning with start of treatment (minus exceptions defined in Section 6.0) must be captured in the Toxicity Form. Baseline AEs should be captured on the Medical History Form.

Participant death due to disease progression should be reported on the Toxicity Form as grade 5 disease progression. If death is due to an AE (e.g. cardiac

disorders: cardiac arrest), report as a grade 5 event under that AE. Participant death must also be recorded on the Death Form.

5.8 Women of Childbearing Potential

Women of childbearing potential (defined as women with regular menses, women with amenorrhea, women with irregular cycles, women using a contraceptive method that precludes withdrawal bleeding, and women who have had a tubal ligation) are required to have a negative serum or urine pregnancy test within 7 days prior to administration of LS301 before inclusion in this study.

5.9 Duration of Study Participation

If at any time the constraints of this protocol are considered to be detrimental to the patient's health and/or the patient no longer wishes to continue in the protocol, the patient should be removed from the study and the reason for discontinuation documented in the case report forms.

Patients will be on study for the duration of the screening process and the surgery or until one of the following criteria applies:

- Death
- Adverse event(s) that, in the judgment of the investigator, may cause severe or permanent harm
- Suspected pregnancy
- Serious noncompliance with the study protocol
- Lost to follow-up
- Patient withdraws consent
- Investigator removes the patient from study
- The Siteman Cancer Center decides to close the study for phase 1A
- The UTSW Department of Surgery or Simmons Comprehensive Cancer Center to close the study for phase 1B and phase 2

Follow-up will continue for 30 days post-surgery (for collection of follow-up lab data).

6.0 REGULATORY AND REPORTING REQUIREMENTS

The entities providing oversight of safety and compliance with the protocol require reporting as outlined below. Please refer to Appendix A for definitions and Appendix B for a grid of reporting timelines.

Adverse events will be tracked for one hour following administration of LS301.

- Baseline adverse events, which shall be recorded on the medical history CRF.
- For purposes of this protocol, adverse events collected and documented on CRFs will not include any events related to surgery.

Refer to the data submission schedule in Section 5.7 for instruction on the collection of AEs in the EDC.

Reporting requirements for Washington University study team may be found in Section 6.1a for phase 1A.

Reporting requirements for UT Southwestern Medical Center study team may be found in Section 6.1b for phase 1B and phase 2.

The Washington University Human Research Protection Office (HRPO) requires that all events meeting the definition of unanticipated problem or serious noncompliance be reported as outlined in Section 6.2 for phase 1A.

The UTSW Human Research Protection Program Office (HRPPO) requires that all events meeting the definition of unanticipated problem or serious noncompliance be reported as outlined in Section 6.2 for phase 1B and phase 2.

The FDA requires that all serious and unexpected adverse events be reported as outlined in Section 6.4. In addition, any fatal or life-threatening adverse experiences where there is a reasonable possibility of relationship to study intervention must be reported.

For the purposes of this study, AEs related to surgery will not be collected or considered reportable.

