5.2.1.3 Definition of Dose-Limiting Toxicities

DLT is defined as any grade 2 or above toxicity that occurs during the hour after injection that is considered possibly, probably, or definitely related to LS301.

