5.2.3 Administration of LS301

The patient will undergo intravenous injection of LS301 4-24 hours prior to surgery. A study nurse or other qualified member of the study team will inject the LS301 via IV over 5-10 minutes in the office or pre-op room (as applicable) and will monitor the patient as described in Section 5.4 below. Administration of LS301 will not interfere with the standard of care, including all standard of care for lymph node assessment using ^{99m}Tc Tilmanocept injection on the day of or day before surgery.

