5.3 Evaluability

All patients who receive an LS301 injection are evaluable for toxicity. Patients are evaluated from time of injection to one-hour post-injection.

Patients enrolled in phase 1 are evaluable for DLT assessment during the hour after injection. Patients in phase 2 will not be assessed for DLT.

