5.4.1 Vital Signs

All vital signs will be recorded on the case report form. Vital signs may be obtained with the subject in the supine or upright position. Care will be taken to obtain subsequent recordings with the subject in the same position (supine or upright). Although allergic or other immediate adverse reactions are not anticipated, subjects will be monitored for at least 60 minutes post injection in an area where emergency equipment is available. Vital signs will be obtained pre-injection (within 30 minutes prior to injection of LS301), within 30 minutes post injection, at 60 minutes post injection, and prior to surgery. Vital signs will include the following: heart rate, systolic blood pressure, diastolic blood pressure, respiratory rate, and body temperature. The following changes from baseline will be considered noteworthy:

- Heart rate > 20 beats per minute
- Systolic blood pressure > 20 mm Hg
- Diastolic blood pressure > 10 mm Hg

Noteworthy changes will be documented on the CRF, and they will be marked as clinically significant or not. If clinically significant, the principal investigator will assess the causality of the change to the injection of LS301. Clinically significant changes in vital signs will be followed up hourly until they return to baseline or normal levels, or until follow-up is no longer warranted. If a clinically significant change of a vital sign is noted, it will be reported on the adverse event log.

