5.4.2 Clinical Laboratory Testing

Laboratory tests will consist of the following: standard CBC, comprehensive metabolic panel and urinalysis obtained at the following time points:

- Baseline: within 30 minutes prior to injection of LS301
- 60 minutes after injection of LS301
- Approximately one hour prior to surgery

Approximately 14 ml of blood and a urine sample will be collected at each time point. For patients enrolled in phase 1B and phase 2 of the study, a portion of the blood samples from each time point will be used to identify the predominant blood protein(s) that binds LS301 and mediates the bioavailability of the agent (refer to Section 5.6). Phase 1B refers to phase 1 study after completing drug safety and selecting optimal dose for testing at 2 and 4 hours from injection to surgery. The current project is that if 3 patients at each of the 3 dose level do not experience adverse events, we will need only 9 patients for the drug safety study (phase 1A) and additional 9 patients at the selected dose for testing at 2, 4, and >12 hours (3 patients for each time point) from injection to surgery.

The results of standard of care laboratory testing obtained up to 30 days post injection will be reviewed. Analysis of this will take into account that the subject has undergone surgical removal of tumor and neoadjuvant treatment including hormonal therapy or chemotherapy.

The following changes from baseline clinical laboratory values are considered to be noteworthy and require assessment as to clinical significance when they fall outside of normal limits. Clinically significant changes in laboratory values should be followed up daily until they return to baseline or normal levels, or until follow-up is no longer warranted. Laboratory values that are abnormal at baseline but move into normal range will not be considered clinically significant. If a clinically significant change of a laboratory value is noted, it will be reported on the AE log.

Analyte	Change from baseline
Hemoglobin	> 2g/dL
WBCs	> 1 K/mm ³
Neutrophils	> 10 %
Lymphocytes	> 10%
Platelets	> 50 K/mm ³
Creatinine	> 0.75 mg/dL
BUN	> 20 mg/dL
Calcium	> 1mg/dL
Sodium	> 5 mmol/L
Potassium	> 0.5 mmol/L
CO ₂	> 4 mmol/L
ALT (SGPT)	> 150 IU/L
AST (SGOT)	> 100 IU/L
Alkaline Phosphatase	> 150 IU/L
Total Bilirubin	> 0.5 mg/dL
Albumin	> 1g/dL

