8.2 Endpoints

8.2.1 Endpoints for Safety Analysis

The primary endpoints of the phase 1 portion of the trial are toxicities and/or adverse events (as outlined in the National Cancer Institute Common Terminology Criteria for Adverse Events version 5.0) recorded after LS301 injection which are definitively or possibly related to the injection. Safety evaluation includes vital signs, clinical laboratory testing and ECG, measured pre- (within 10-15 minutes or 30 minutes of injection) and post-injection (within 30 minutes or/and at ~60 minutes). Noteworthy post-versus-pre changes in all the safety measures will be recorded while clinically significant changes will be reported as adverse events in accordance to HRPO requirements. All the safety endpoints are described in detail in Section 5.4 and adverse events detailed in Section 6.0.

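### Adverse events are tracked for one hour, but other sections log safety findings from pre-surgery and 30-day data, and no section says which period feeds the phase 1 safety summary

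*Combined protocol and SAP*

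**What the plan says.** **Text that stops at one hour**
- Section 6.0: "Adverse events will be tracked for one hour following administration of LS301".
- Section 5.3, on evaluability for toxicity: "Patients are evaluated from time of injection to one-hour post-injection".

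**Text that runs longer**
- Section 5.4.1 takes vital signs within 30 minutes, then "at 60 minutes post injection, and prior to surgery". Clinically significant changes go on the adverse event log, with no time limit.
- Section 5.4.2 draws blood at 60 minutes and about one hour before surgery, and reviews standard-of-care laboratory results up to 30 days after injection. Its rule is: "If a clinically significant change of a laboratory value is noted, it will be reported on the AE log". This too has no time limit. Urinalysis changes are noted but not used to judge clinical significance.
- Section 5.7 makes the Toxicity Form continuous. Section 5.7.1 requires capture of "All adverse events that occur beginning with start of treatment", less the exceptions in Section 6.0, and gives no end time.
- Section 5.9 continues follow-up for laboratory data to 30 days after surgery.

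**The analysis text**
- Section 8.2.1 makes related toxicities and adverse events recorded after injection the phase 1 primary endpoint, with no end time. It lists the safety measures as "post-injection (within 30 minutes or/and at ~60 minutes", and refers the reader to both Section 5.4 and Section 6.0.
- Section 8.3.1 counts adverse events and compares vital signs before and after injection. It names no AE window and no laboratory analysis.

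**The concern.** Safety is the phase 1 primary objective of a first-in-human agent, and the phase 1 data go to the FDA before phase 2 opens. A clinically significant laboratory change found just before surgery belongs on the AE log under Section 5.4.2, but falls after tracking has ended under Section 6.0. Two study teams could each follow the protocol and produce different AE counts. That risk is practical here, because phase 1A runs at one institution and phases 1B and 2 at another.

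Laboratory findings are the most exposed. Section 8.3.1 contains no analysis of laboratory values, so an AE entry is their only specified route into the safety summary. Pre-surgery vital signs might still enter through the before-and-after comparison, although 8.3.1 does not say which post-injection reading it uses.

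**Working it through.** The plan states no figure on this point, so the check sets the sections side by side and adds simple timing arithmetic.

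**1. Where the later assessments fall.** Section 5.2.3 gives the interval: "The patient will undergo intravenous injection of LS301 4-24 hours prior to surgery". Section 5.4.2 places the last draw about one hour before surgery.
- Surgery at 4 h: draw at 4 − 1 = 3 h. Surgery at 24 h: draw at 24 − 1 = 23 h.
- Section 5.4.2 also describes phase 1B groups at 2, 4 and more than 12 hours. For the 2-hour group the draw falls at 2 − 1 = 1 h, the edge of the window. That 2-hour timing itself disagrees with the 4–24 hours elsewhere and needs reconciling.
- One hour is 1/4 = 25% of the shortest and 1/24 = 4.2% of the longest injection-to-surgery interval on the 4–24 hour schedule.

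| Post-injection safety data | Time after injection (4–24 h schedule) | Within one hour? |
|---|---|---|
| Vital signs, ECGs and blood tests up to 60 min | up to 1 h | yes |
| Vital signs before surgery | after the 60-min reading, before surgery at 4–24 h | no |
| Blood tests before surgery | about 3–23 h | no |
| Standard-of-care laboratory review | to 30 days | no, apart from any result within the hour |

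One of the two scheduled post-injection blood draws is therefore outside the hour on this schedule.

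**2. Whether the cross-references settle it.** Section 5.7.1 defers to exceptions in 6.0, and 6.0 sends the reader back to 5.7 for AE collection. The exceptions that 6.0 sets out are baseline events and surgery-related events. Excluding surgery-related events would be unnecessary if collection really ended at one hour, since surgery comes later. Section 5.7.1 also requires deaths from disease progression on the Toxicity Form, which fits poorly with a one-hour period. The references are circular and no sentence gives precedence.

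**3. Whether the surgery exclusion removes the conflict.** It does not for the pre-surgery assessments, which precede surgery. It does bear on the 30-day results.

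**4. The 30-day end point.** Section 5.4.2 counts from injection and Section 5.9 from surgery. On the 4–24 hour schedule these differ by 4 to 24 hours: small, but two different cut-offs.

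**5. Possible effect on counts (illustration only).** The nearest stated figures are in the Section 8.4 DLT table, which reproduces: P(X ≥ 3 of 9) = 0.262 at a 20% rate and 0.537 at 30%. Apply the same formula to patients with a related adverse event, and assume that a share f of those events arises in the first hour. The recorded rate is then p × f. The documents give no value for f.

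| True rate p | f = 100% | 75% | 50% | 25% |
|---|---|---|---|---|
| 20% | 0.262 | 0.141 | 0.053 | 0.008 |
| 30% | 0.537 | 0.330 | 0.141 | 0.025 |

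If everything arises in the first hour, nothing is lost.

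**The case against.** The best reply is that the rules can coexist: general AE tracking lasts an hour, and later clinically significant vital-sign or laboratory changes are still logged. That is workable, so it would be too strong to say that the rules cannot all be followed. But it is one reading among several. The protocol does not state it, and 8.3.1 does not say whether such later entries are counted.

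It is also fair that the FDA safety-reporting rules in Sections 6.1.3 and 6.2.3 and Appendix B have no one-hour limit, so serious suspected reactions are not lost to the FDA. This stands, and confines the problem to the safety summary.

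Several stronger readings are tempting but unsupported:
- *Section 8.2.1 limits the endpoint to 30 and 60 minutes.* Its endpoint sentence has no end time; only the listed measurements stop there, and it also points to Section 5.4. It is ambiguous, not limiting.
- *The dog creatinine rise at 4 and 24 hours shows late toxicity.* Section 1.8.2 attributes it to probable assay interference and says that creatinine was not measured earlier.
- *The mouse lung foci (16 of 20 treated animals) show late onset.* Day 2 was the first sacrifice, so onset is unknown, and the foci were absent at Day 14. The dose was 7.5 mg/kg. On the conversion in Section 1.10 (0.006/0.075 = 0.08) that is 7.5 × 0.08 = 0.6 mg/kg human-equivalent, six times the top trial dose. Other animal signals fell early: a neutrophil fall at 5–60 minutes in one dog, and vomiting soon after infusion in one of the dogs.
- *The dog half-life of 4.8 h implies late toxicity.* 0.5^(1/4.8) = 0.866, so about 87% of the plasma level would remain at one hour if humans matched dogs. That describes plasma persistence, not adverse events.

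Finally, only vital signs and laboratory results are collected after the hour. Symptoms between one hour and surgery have no scheduled assessment, and no table can recover them.

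**Conclusion.** The inconsistency is real and lies in current text. Sections 5.3 and 6.0 end toxicity evaluation and AE tracking at one hour. Sections 5.4.1 and 5.4.2 require later log entries, and nothing says which governs. If the one-hour rule is applied, measured toxicity can be omitted from the phase 1 primary safety summary. This affects the pre-surgery blood draw at about 3 to 23 hours on the 4–24 hour schedule, and later laboratory review. The gap is smallest for the 2-hour phase 1B group.

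The word is *can*: read alone, Sections 5.4 and 5.7.1 would retain these events. The number of events at risk is unknown, and the illustration rests on assumed first-hour shares.

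A reader might also infer that dose-escalation decisions are compromised. The documents do not show that. The DLT has its own definition, "DLT is defined as any grade 2 or above toxicity that occurs during the hour after injection", and Section 5.3 agrees with it.

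**What to change.** 1. Reconcile Sections 5.3, 6.0 and 8.2.1 with 5.4.1, 5.4.2, 5.7, 5.7.1 and 5.9 so that one AE collection period is stated. Say whether the 30 days run from injection or from surgery, and replace the circular references between 5.7 and 6.0 with one governing sentence.
2. In 8.2.1, state which time points feed the primary safety endpoint.
3. In 8.3.1, tabulate every AE-log entry from injection to the last safety assessment already scheduled or reviewed, overall and by dose level. Split it into 0–1 h, 1 h to surgery, and after surgery. Handle surgery-related events as Section 6.0 states, and show attribution to LS301, because Section 5.4.2 acknowledges that surgery and other therapy affect the 30-day results.
4. State that symptoms after the first hour have no scheduled assessment, so that the later columns are not read as complete.

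The one-hour DLT window, and the length of the collection period, remain for the clinical team.

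The cost is amendment wording and a few table rows. No visit or test is added.
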